5.3.2 Patient-reported outcomes endpoints

- Absolute change in child self-reported and parent impact KIT scores from baseline to 1 week, 4 weeks, 12 weeks, and 1 year after study enrollment
- Absolute change in Hockenberry fatigue (FS-C, FS-A, FS-P) scores from baseline to 1 week, 4 weeks, 12 weeks, and 1 year after study enrollment
- Global Change Scale scores at 1 week, 4 weeks, 12 weeks, and 1 year after study enrollment

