3.2 Secondary Objectives

- 3.2.1 To compare the proportion of patients with poor bleeding scores (WHO Bleeding Scale \geq 2 or Modified Buchanan Score \geq 3) at 1, 2, 3, 4, 12 weeks and 1 year in patients with newly diagnosed ITP treated with eltrombopag vs. standard first-line agents
- 3.2.2 To compare the cumulative number of rescue therapies (defined in section 8.4) needed during the first 12 weeks of treatment for patients with newly diagnosed ITP treated with eltrombopag vs. those treated with standard first-line agents
- 3.2.3 To compare platelet response during weeks 6-12 of study in patients treated with eltrombopag vs standard first line agents who required a rescue treatment during weeks 1-2 of study
- 3.2.4 To compare the proportion of patients who do not need ongoing treatment at 12 weeks and 6 months for patients with newly diagnosed ITP treated with eltrombopag vs. those treated with standard first-line agents
- 3.2.5 To compare the proportion of patients with a treatment response (4 binary endpoints (section 5.2.5)) at one year after study enrollment in patients with newly diagnosed ITP treated with eltrombopag vs. those treated with standard first-line agents
- 3.2.6 To compare the number of 2nd-line therapies (defined in section 7.2.1) used in weeks 13-52 for patients with newly diagnosed with ITP treated with eltrombopag vs. those treated with standard first-line agents
- 3.2.7 To compare the absolute change in percentage of CD4 $^{+}$ 25 $^{+}$ Foxp3 $^{+}$ regulatory T cells (Tregs) a) from baseline to 12 weeks; and b) from baseline to 1 year, in patients with newly diagnosed ITP treated with eltrombopag vs. those treated with standard first-line agents
- 3.2.8 To compare change in Health Related Quality of Life (HRQoL) from a) baseline to 1 week, b) baseline to 4 weeks, c) baseline to 12 weeks, and, d) baseline to 1 year, as measured by the parent-proxy report of the Kids ITP tools (KIT) and Global Change Scale for patients with newly diagnosed ITP treated with eltrombopag vs. those treated with standard first-line agents
- 3.2.9 To compare fatigue at 1 week, 4 weeks, 12 weeks, and 1 year as measured by the parent-proxy report of the Hockenberry Fatigue Scale-Parent (FS-P)

for patients with newly diagnosed ITP treated with eltrombopag vs. those treated with standard first-line agents

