5.2 Secondary Endpoints

- 5.2.1 Poor bleeding score (binary) at 1, 2, 3, 4 weeks, 12 weeks, and 1 year after study enrollment defined as WHO Bleeding Scale ≥ 2 or Modified Buchanan Scale ≥ 3
- 5.2.2 Cumulative number of rescue therapies required during the first 12 weeks of treatment
- 5.2.3 Platelet response (binary), defined as ≥ 3 of 4 weeks with platelets $>50 \times 10^9/L$ during weeks 6-12 of therapy, but patient required a rescue treatment during weeks 1-2 of study
- 5.2.4 No further need for treatment (binary) after 12 weeks or 6 months of study
- 5.2.5 Treatment response (binary endpoints) at 1 year defined as:
 - **CR** is defined as platelet count $>/= 150 \times 10^9/L$
 - **Primary Remission** at 1 year is defined as CR at 1 year with no second-line agents required and $>/= 3$ months after discontinuing most recent platelet active medication
 - **Disease resolution** at 1 year is defined as CR at 1 year $>/= 3$ months after discontinuing most recent platelet active medication. May have received a second-line therapy, excluding rituximab or splenectomy.
 - **Disease stability** at 1 year is defined as platelets $>/= 50 \times 10^9/L$ but $<150 \times 10^9/L$ $>/= 3$ months after discontinuing most recent platelet active medication.
- 5.2.6 Number of 2nd-line therapies (defined in section 7.2.1) in weeks 13-52
- 5.2.7 Absolute change in percentage of CD4⁺25⁺Foxp3⁺ regulatory T cells from baseline at 12 weeks and 1 year
- 5.2.8 Absolute change in parent proxy-reported KIT overall scores from baseline to 1 week, 4 weeks, 12 weeks, and 1 year after study enrollment (see Appendix A2)
- 5.2.9 Total scale intensity ratings (continuous) from the Hockenberry Fatigue Scale-Parent (FS-P) at 1 week, 4 weeks, 12 weeks, and 1 year (see Appendix A2)
- 5.2.10 Serum iron, TIBC, transferrin saturation, ferritin, MCV, and hemoglobin at 12 weeks, 6 months, and 1 year after study enrollment
- 5.2.11 Safety evaluations as defined by:
 - Abnormal LFTs:
 - ALT $\geq 3x$ ULN in patients with normal baseline
 - ALT $\geq 3x$ baseline or $\geq 5x$ ULN (whichever is lower) in patients with abnormal baseline
 - ALT $\geq 3x$ ULN AND bilirubin $\geq 1.5 \times$ ULN ($>35\%$ direct)

- Incidence of adverse events (see section 9.1.6)
- Incidence of serious adverse events (see section 12.2)

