To address secondary objective 3.2.2, an ANCOVA model will be used to compare the number of rescue therapies between the two arms.

To address secondary objective 3.2.3, the observed proportion and 95% confidence interval of platelet responders will be calculated in the subset of patients who required a rescue treatment during weeks 1-2 of the study.

To address secondary objective 3.2.4, the Cochran-Mantel-Haenszel test will be used to compare the proportion of patients who do not need ongoing treatment at 12 weeks and 6 months between the two arms.

To address secondary objective 3.2.5, the Cochran-Mantel-Haenszel test will be used to compare the proportion of patients with a treatment response at one year between the two arms.

To address secondary objective 3.2.6, an ANCOVA model will be used to compare the number of 2nd-line therapies between the two arms

To address secondary objective 3.2.7, an ANCOVA model will be used to compare the absolute change from baseline in percentage of regulatory T cells at 12 weeks and 1 year between the two arms

To address secondary objective 3.2.8, KIT scores will be calculated as per the methods described in Klaassen et al.²⁸ Spaghetti plots will be used to visualize the KIT scores over time per patient by treatment arm. An ANCOVA model will be used to compare the absolute change from baseline in KIT overall score at 1 week, 4 weeks, 12 weeks, and 1 year between the two arms. An ANCOVA model will be used to compare the Change Scale score at 1 week, 4 weeks, 12 weeks, and 1 year between the two arms.

To address secondary objective 3.2.9, fatigue scores will be calculated as per the methods described in Hockenberry et al.²⁹ All measures will be rescaled from 0 (no fatigue) to 100 (high fatigue) for consistency in scoring. Spaghetti plots will be used to visualize the fatigue scores over time per patient by treatment arm. The PROMIS tired question: “My child (I) got tired easily never to almost always” will be used as an anchor with severe fatigue defined as “often” or “almost always” with moderate fatigue being “sometimes”. An ANCOVA model will be used to compare the absolute change from baseline in fatigue at 1 week, 4 weeks, 12 weeks, and 1 year between the two arms.

To address secondary objective 3.2.10, an ANCOVA model will be used to compare iron indices at 12 weeks, 6 months, and 1 year between the two arms

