To address secondary objective 3.2.11, the frequency and proportion (with 95% confidence interval) of patients with abnormal LFTs will be calculated. Adverse event rates will be coded by body system and MedDra classification term. Adverse events and serious adverse events will be tabulated by treatment group and will include the number of patients for whom the event occurred, the rate of occurrence, and the severity and relationship to study drug. If a patient experiences the same toxicity multiple times, a patient will be counted only once for a given toxicity at the maximum grade.

d. Analysis of Exploratory Objectives

Exploratory objectives are hypothesis-generating only. Any exploratory findings need to be confirmed in an independent study.

To address the platelet exploratory objectives 3.3.1, a Cochran-Mantel-Haenszel test will be used to compare the proportion of patients between treatment arms with: (1) specific platelet-defined treatment response at 12 weeks, (2) extreme thrombocytosis, and (3) loss of treatment response (in the subgroup of patients who achieved treatment response during the first 12 weeks. Cumulative incidence curves by treatment arm will be created to describe: (1) time to response and (2) time to platelet and bleeding response. Gray's test will be used to compare the cumulative incidence between treatment arms.

To address the patient-reported outcomes exploratory objectives 3.3.2, KIT scores and fatigue scores will be calculated as described. Spaghetti plots will be used to visualize the scores over time per patient by treatment arm. An ANCOVA model will be used to compare the absolute change from baseline at 1 week, 4 weeks, 12 weeks, and 1 year between the two arms.

To analyze the non-survey endpoints of exploratory objective 3.3.3, a Cochran-Mantel-Haenszel test (for categorical outcomes) or an ANCOVA model (for

continuous outcomes, like the cost of therapy) will be used to compare the two arms.

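### FS-P fatigue is defined as a score but analysed as a change, and both it and the Global Change Scale sit in two endpoint tiers; one tier, one variable and a named baseline covariate would settle it (minor)

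*Combined protocol and SAP*

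**What the plan says.** **Fatigue.** Objective 3.2.9 compares FS-P fatigue at 1, 4 and 12 weeks and 1 year, and endpoint 5.2.9 is the FS-P total score at those visits. For this objective, section 16.c says an ANCOVA will "compare the absolute change from baseline in fatigue at 1 week" and at the later visits. Section 5.3.2 lists as exploratory "Absolute change in Hockenberry fatigue (FS-C, FS-A, FS-P) scores from baseline to 1 week" and to the same later visits.

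**Global Change Scale.** Objective 3.2.8 measures quality of life by the "parent-proxy report of the Kids ITP tools (KIT) and Global Change Scale". Under that objective 16.c states: "An ANCOVA model will be used to compare the Change Scale score", at four visits. Endpoint 5.2.8 covers the KIT overall score only, and no other item in 5.2 mentions the Change Scale. Section 5.3.2 lists it as exploratory: "Global Change Scale scores at 1 week, 4 weeks, 12 weeks, and 1 year after study enrollment".

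**Rules that apply to both.** Section 16.c tests each secondary endpoint for normality and moves continuous endpoints to a Wilcoxon rank-sum test if normality fails. Section 16 names no covariates for any ANCOVA. Section 16.d treats exploratory objectives as generating hypotheses only and adds: "Any exploratory findings need to be confirmed in an independent study". No such limit is written for secondary results, and no alpha or multiplicity rule is given for them.

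**The concern.** A reader of the final report should be able to tell which tier a patient-reported result belongs to and which variable was compared. Here the documents give two answers on tier for both measures, and two answers on variable for FS-P. The secondary FS-P endpoint as defined has no matching analysis, while the variable that is analysed also stands in the exploratory list.

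The tier decides how a result is read, because 16.d attaches a need for confirmation to exploratory findings. The variable can decide whether the FS-P comparison is significant, if the analysis is not adjusted for baseline. The trial is open label and the reports come from parents, so the plan gains from leaving neither question open.

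**Working it through.** **Step 1: set the sections side by side.**

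| Measure | Objective | Endpoint in 5.2 | Analysis in 16.c | Listed in 5.3.2 |
|---|---|---|---|---|
| FS-P | 3.2.9: fatigue at each visit | 5.2.9: score at each visit | change from baseline | yes, as change |
| Global Change Scale | 3.2.8, with KIT | none (5.2.8 is KIT only) | score, ANCOVA | yes |

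No section says which listing prevails. Exploratory objective 3.3.2 and the matching sentence in 16.d name KIT and fatigue scores, not the Change Scale.

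**Step 2: does score versus change matter for FS-P?** Let x be the baseline score and y the visit score. If x is a covariate, replacing y by y − x lowers the coefficient of x by exactly 1 and leaves the treatment coefficient, residuals and p-value unchanged. In one simulated data set the adjusted estimate was 0.1998 (p = 0.254) for both variables. Without x, score gave 0.2015 (p = 0.297) and change gave 0.1977 (p = 0.326).

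**Step 3: how far apart are the unadjusted versions?** Inputs:
- 98 versus 49 patients. This is the informative count from the sample-size section, used here as an assumption. Secondary analyses use evaluable patients, and section 9.3 gives the fatigue scales in English only, so FS-P numbers will differ.
- Correlation r between baseline and visit of 0.3, 0.5 and 0.7, equal SDs, and shift δ in SD units. None of these is in the documents.
- Two-sided 0.05.

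Relative variance is 1 for score, 2(1 − r) for change and 1 − r² for baseline-adjusted ANCOVA:
- r = 0.3: 1, 1.4 and 0.91
- r = 0.5: 1, 1.0 and 0.75
- r = 0.7: 1, 0.6 and 0.51

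ANCOVA has the smallest variance each time.

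The expected z is δ × √(49 × 98 / 147) = 5.715δ for score, and 5.715δ / √(2(1 − r)) for change. The two z statistics correlate at √((1 − r)/2), which is 0.592, 0.500 and 0.387. The probability that exactly one of them exceeds 1.96 in absolute value is:

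| δ | r = 0.3 | r = 0.5 | r = 0.7 |
|---|---|---|---|
| 0 | 7.6% | 8.1% | 8.7% |
| 0.3 | 28.7% | 32.3% | 40.3% |
| 0.5 | 25.8% | 21.4% | 18.7% |
| 0.8 | 2.9% | 0.8% | 0.5% |

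At δ = 0.5, power for r = 0.3, 0.5 and 0.7 is:
- score: 81.5% throughout
- change: 67.6%, 81.5% and 95.8%
- baseline-adjusted ANCOVA: 85.0%, 91.0% and 97.9%

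**Step 4: the Wilcoxon test itself, by simulation.** On normal data at δ = 0.5 the two versions disagree in about 28%, 24% and 21% of trials. On skewed scores with no effect they disagree in 7.1% to 9.5%, and at least one is significant in 8.1% to 9.9% rather than 5%.

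**Step 5: is the fallback needed when scores are skewed?** In a simulation of skewed, bounded scores with a 0.5 SD shift, baseline-adjusted ANCOVA had power of 82%, 87% and 95%. Wilcoxon on change had 57%, 71% and 89%. The type I error of the ANCOVA was about 4 to 5%.

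**The case against.** The strongest reply is that 16.c already fixes one variable and one model for objective 3.2.9. No analysis of the unadjusted score is written anywhere, so reporting one would be a visible departure. Baseline is also the natural covariate in an ANCOVA of change, and with it the question of score or change disappears. This stands as far as it goes. What remains is that the covariate is not named, the fallback drops it, and the endpoint definition still says score.

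For the Change Scale, section 9.3 describes a parent and a child version. Parent secondary and child exploratory would fit the way 5.3.2 handles KIT. That is plausible but unstated, and it cannot explain FS-P, which 5.3.2 names outright.

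A reader might infer that the status and result of both measures can be chosen after the data are seen. The documents do not support that. The analysis text commits to FS-P change by ANCOVA, and no alpha is tied to either tier. Nor do they say that a secondary result is free of any need for confirmation; they are silent on it.

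A reader might also infer that the plan intends a change-from-baseline analysis of the Change Scale, which has no baseline value. It does not: 16.c compares the score itself, and the change-from-baseline sentence in 16.d covers only KIT and fatigue scores.

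**Conclusion.** The inconsistencies are real and the consequence is limited, so this is a minor point. For both measures the tier affects interpretation only. For FS-P the choice of variable can alter significance, but only if baseline is left out of the ANCOVA or the Wilcoxon fallback is used.

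In that case the two versions disagree in about 7 to 9% of trials under no effect and about 20 to 40% at shifts of 0.3 to 0.5 SD. At 0.8 SD the disagreement is 3% or less, so these figures depend on the effect assumed as well as on the correlation and on 98 versus 49 patients. The identity of score and change under baseline adjustment needs none of those assumptions. The primary endpoint is not touched.

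**What to change.** (a) **FS-P.** In 16.c, specify ANCOVA with baseline FS-P and the randomisation strata (age group and up-front treatment status) as covariates, and keep this adjusted analysis rather than switching to the unadjusted Wilcoxon test. Align 3.2.9, 5.2.9 and 16.c on one variable. Either will do once baseline is a covariate; the score needs the fewest edits, since 3.2.9 and 5.2.9 already use it. Delete FS-P from 5.3.2.

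(b) **Global Change Scale.** Add the parent-proxy version to 5.2.8 and restrict 5.3.2 to the child self-report version, with a clause in 16.d saying how the child version is compared. An ordinal analysis of its seven categories is optional.

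The cost is a few wording changes in 3.2.9 or 5.2.9 (if change is chosen), 5.2.8, 5.3.2, 16.c and 16.d. No new data are needed.

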5.3.3 Cost of therapy endpoints

- Number of hospitalizations

6 SUBJECT SELECTION

Subjects with a diagnosis of ITP who meet the inclusion and exclusion criteria will be eligible for participation in this study.

6.1 Inclusion Criteria

- Age: 1- <18 years
- Newly diagnosed ITP (<3 months from diagnosis (first abnormal platelet count), per international working group definition¹⁷)
- Platelets $<30 \times 10^9/L$ at screening
- Requires pharmacologic treatment from the perspective of the treating clinician.
Need to treat is at the discretion of the investigator, but there should be clinical

equipoise about the use of eltrombopag vs standard treatment options (patients should not, in the opinion of the investigator, require concomitant therapy at time of enrollment).

- Treatment options include one of three standard therapies, (IVIg, steroids, or Anti-D). *For example, if patient has previously shown no response to IVIg or steroids and is Rh-negative, patient would not be eligible for study.*
- Patient population includes both:
 - **1) Upfront treatment:** Patient within 10 days of ITP diagnosis who has not received previous treatment **OR**
 - **2) Treatment failure:** Patients who have failed standard management (observation or treatment with one or more first-line agents)
 - *Failure of observation: no platelet recovery (>30 x10⁹/L) with observation >10 days from diagnosis, with need to treat*
 - *Poor response to first-line agent (platelets remain <30 x10⁹/L)*
 - *Initial response to first-line agent, but response wanes and platelets fall below 30 x10⁹/L*
- Family willing and able to return for required lab studies

6.2 Exclusion Criteria

- Severe bleeding: Buchanan Overall Grade 4 or 5 bleeding (see Appendix A1), or severe bleeding requiring emergent treatment at the discretion of the provider. (e.g., intracranial hemorrhage, pulmonary hemorrhage, bleeding with ongoing need for pRBC transfusion)
- Prior treatment with TPO-RA (eltrombopag or romiplostim)
- Known secondary ITP (due to lupus, CVID, ALPS)
- Known HIV (or history of HIV positivity) or Hepatitis C (screening not required if no clinical suspicion)
- Evans Syndrome: positive direct Coombs with evidence of active hemolysis (elevated LDH or reticulocyte count not attributable to recent treatment or bleeding)
- Any Malignancy
- History of stem cell transplant or solid organ transplant
- AST or ALT >2x ULN
- Total bilirubin >1.5 × ULN
- Subjects with liver cirrhosis (as determined by the investigator)
- Creatinine >2.5 × upper limit of normal (ULN)
- Known active or uncontrolled infections not responding to appropriate therapy
- On anticoagulation or anti-platelet agents
- Known thrombophilic risk factors. *Exception: Subjects for whom the potential benefits of participating in the study outweigh the potential risks of thromboembolic events, as determined by the investigator.*
- Baseline ophthalmic problems that may potentiate cataract development
- Impaired cardiac function, such as:

- Known prolonged QTc, with corrected QTc >450 msec
 - Other clinically significant cardio-vascular disease (e.g., uncontrolled hypertension, history of labile hypertension),
 - History of known structural abnormalities (e.g. cardiomyopathy).
- History or current diagnosis of cardiac disease indicating significant risk of safety for patients participating in the study such as uncontrolled or significant cardiac disease, including any of the following:
 - Recent myocardial infarction (within last 6 months),
 - Uncontrolled congestive heart failure,
 - Unstable angina (within last 6 months),
 - Clinically significant (symptomatic) cardiac arrhythmias (e.g., sustained ventricular tachycardia, and clinically significant second or third degree AV block without a pacemaker.)
 - Long QT syndrome, family history of idiopathic sudden death, congenital long QT syndrome or additional risk factors for cardiac repolarization abnormality, as determined by the investigator.
- Known immediate or delayed hypersensitivity reaction to eltrombopag or its excipient.
- Pregnant, breastfeeding, or unwilling to practice birth control during participation in the study. *Women of childbearing potential (have achieved menarche) must have a negative serum or urine pregnancy test and agree to use basic methods of contraception (if sexually active) or maintain abstinence for the duration of the study until 7 days after the last dose of study treatment. Basic contraception methods include:*
 - *Total abstinence (when this is in line with the preferred and usual lifestyle of the subject. Periodic abstinence (e.g., calendar, ovulation, symptothermal, post-ovulation methods) and withdrawal are not acceptable methods of contraception*
 - *Female sterilization (have had surgical bilateral oophorectomy with or without hysterectomy), total hysterectomy, or tubal ligation at least six weeks before taking study treatment. In case of oophorectomy alone, only when the reproductive status of the woman has been confirmed by follow up hormone level assessment*
 - *Male sterilization (at least 6 months prior to screening). The vasectomized male partner should be the sole partner for that subject*
 - *Barrier methods of contraception: Condom or Occlusive cap. For the UK: with spermicidal foam/gel/film/cream/ vaginal suppository*
 - *Use of oral, injected or implanted hormonal methods of contraception or placement of an intrauterine device (IUD) or intrauterine system (IUS), or other forms of hormonal contraception that have comparable efficacy (failure rate <1%), for example hormone vaginal ring or transdermal*

hormone contraception. In case of use of oral contraception women should have been stable on the same pill for a minimum of 3 months before taking study treatment.

- Male patients who are sexually active and do not agree to abstinence or to use a condom during intercourse while taking eltrombopag, and for 7 days after the last dose of study treatment.
- History of alcohol/drug abuse
- Presence of a medical condition that in the opinion of the Investigator would compromise the safety of the patient or the quality of the data.
- Concurrent participation in an investigational study within 30 days prior to enrollment or within 5-half-lives of the investigational product, whichever is longer. Note: parallel enrollment in a non-therapeutic trial such as disease registry or biology study is permitted.

